# 6 Trial design and setting

This trial is a longitudinal observational study of physical activity and physical fitness in 120 people with early-mid stage HD (assessed as having an overall low risk) with an additional nested evaluation of a 12-month physical activity intervention (n=30) compared to usual activity (n=30).

Participants will be recruited from current Enroll-HD sites in Europe and the USA. Enroll-HD is a worldwide research platform that has as its core a longitudinal observational study of HD families. Enroll-HD provides an infrastructure to support clinical studies such as the one proposed here. Recruitment for the longitudinal study and the nested RCT will be conducted over a period of 15 months, both with a 12 month follow up period. The trial is expected to last a total of 27 months. The end of the trial will be defined as last participant, last visit, which will be the 12-month assessment. This could be a participant in either the observational cohort or nested RCT.

All participants will undergo a baseline assessment as part of their annual Enroll-HD visit where standard measures will be collected as per the Enroll-HD study protocol. Additional assessments pertaining to physical activity will also be performed (see section 12.1 for further details). The additional assessments should be collected  $\pm$  4 weeks of the annual ENROLL visit. These assessments will be repeated after 12 months within  $\pm$  4 weeks of the next annual Enroll-HD visit. For those participants taking part in the nested RCT, an additional assessment will be performed at 6 months. For participants randomised to receive the physical activity and coaching intervention in the nested RCT, they will receive the intervention over a 12-month period which will include 18 home or site visits (pragmatically scheduled) and additional supportive monthly telephone calls.

All data will be entered directly into the trial database by local researchers via an individual log-in. Where data is obtained from third party sources exports will be obtained on a monthly basis for upload into the trial database.

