# 14.3 Sample size

The primary outcome for this trial is feasibility of a within cohort nested RCT of a 12-month exercise intervention in terms of; data completeness, recruitment, retention, fidelity and acceptability. For a total sample size of 120 participants recruited into the cohort study we are able to determine a 95% confidence interval for 70% retention rate to within +/- 8.2%.

In line with the primary feasibility objectives of the trial a formal calculation has not been carried out to determine the sample size for the RCT. Formal hypotheses testing will not be carried out and only effect sizes and 95% confidence intervals will be provided for the interpretation of outcomes

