#### a. Feasibility

Summary data for recruitment, retention and data completeness will be tabulated for the cohort and nested RCT. Adherence rates, safety and fidelity will also be summarised for the RCT.

b. RCT

The individually randomised data from the three sites will be explored.

The analysis will compare

- I. Linked Enroll-HD data for participants between the two groups at 1 year
- II. PACE-HD trial data (see section 12.1)

Linear models will be used for key continuous outcomes, controlling for individual participant characteristics used to balance the randomisation as baseline covariates. Treatment effects will be summarised using regression coefficients, 95% confidence intervals and standardised effect sizes. Standard diagnostics will be performed to ensure adequate model fit (including inspecting fitted versus residual plots). The analysis will be intention to treat and complete case.

Analysis of secondary outcomes will proceed similarly, with linear regression used for continuous outcomes and logistic regression for dichotomous outcomes. A mediation analysis will be performed on the physical fitness measure recorded at 6 months. No inflation for clustering has been included in the power calculation however a sensitivity analysis will be conducted using hierarchical modelling to explore the extent of clustering in the primary outcome variable by site.

Progression criteria to proceed to further evaluation will be based on the following; over 60% drop out from the RCT at 12 months will mean no progression, between 40 and 60 % drop out will mean that changes to the intervention and/or follow-up procedures will be required and less than 30% drop at 12 months will indicate that the intervention is suitable for further evaluation without modification.

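### The progression rule assigns no outcome to RCT drop-out from 30% to under 40%, which leaves the choice between modifying and proceeding unchanged open until the data are known

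*Protocol*

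**What the plan says.** The primary objective is feasibility (Protocol sections 5.1 and 5.3), and section 15.1 states how drop-out will decide on further evaluation. It gives three outcomes:

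- Stop: "over 60% drop out from the RCT at 12 months will mean no progression".
- Modify, followed directly by the start of the proceed limit: "between 40 and 60 % drop out will mean that changes to the intervention and/or follow-up procedures will be required and less than 30" per cent.
- Proceed, in full: "less than 30% drop at 12 months will indicate that the intervention is suitable for further evaluation without modification".

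Section 6 gives the size of the randomised part: "nested evaluation of a 12-month physical activity intervention (n=30) compared to usual activity (n=30"), so 60 in total.

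The only retention rate that the protocol names is in section 14.3. There it supports a precision statement on the cohort: "For a total sample size of 120 participants recruited into the cohort study", the authors expect to estimate a "95% confidence interval for 70% retention rate to within +/- 8.2" percentage points. The same section says that the RCT size does not come from a formal calculation.

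Two other sections bear on what counts as drop-out. Section 5.3 measures retention as the share of people who finish the intervention. Section 10.2 treats an RCT participant as lost to follow-up after missing more than four coaching contacts in a row.

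**The concern.** The modify band starts at 40% and the proceed band ends just below 30%. A drop-out of 30% or more but less than 40% belongs to neither, and it is not a stop. No other section of the protocol fills the band. The thresholds are fixed in the protocol itself, so this is not a detail left to the statistical analysis plan.

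This is the only stated decision rule for the primary objective, and drop-out is its only criterion. The trial is open-label for participants and assessors (section 14.2) and has no data monitoring committee (section 22.3). If the result falls in the gap, people who already know the data will choose between modifying the intervention or follow-up and going forward unchanged. Progression criteria are set in advance to avoid exactly that.

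**Working it through.** **Inputs.** Thresholds of 60%, 40 to 60%, and strictly under 30% (section 15.1). RCT size 30 + 30 = 60 (section 6). Retention of 70% with n = 120 and a stated half-width of 8.2 points (section 14.3). The true RCT drop-out is not given anywhere, so I take 20% to 40% as an assumed range.

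**The plan's own figure.** Wald half-width = 1.96 × √(0.70 × 0.30 / 120) = 1.96 × 0.04183 = 0.0820, or 8.2 points. It reproduces. It describes the cohort of 120. For the 60 in the RCT the same formula gives 1.96 × √(0.21 / 60) = 0.116, or 11.6 points.

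**Bands as counts out of 60.**

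- Under 30%: 0.30 × 60 = 18, so 0 to 17 drop-outs (proceed).
- 30% to under 40%: 0.40 × 60 = 24, so 18 to 23 drop-outs (no outcome assigned).
- 40% to 60%: 24 to 36 drop-outs (modify).
- Over 60%: 37 or more (stop).

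**Chance of each result.** With X the number of drop-outs, X ~ Binomial(60, p), and P(gap) = Σ C(60, x) pˣ (1 − p)⁶⁰⁻ˣ for x = 18 to 23.

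| True drop-out | Proceed (0–17) | No outcome (18–23) | Modify (24–36) | Stop (37+) |
|---|---|---|---|---|
| 20% | 0.957 | 0.042 | <0.001 | <0.001 |
| 25% | 0.775 | 0.217 | 0.007 | <0.001 |
| 30% | 0.451 | 0.485 | 0.063 | <0.001 |
| 35% | 0.172 | 0.581 | 0.247 | <0.001 |
| 40% | 0.041 | 0.410 | 0.548 | 0.001 |

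At true drop-out of 30% or 35%, having no assigned outcome is the single most likely result.

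**If only the intervention arm is counted.** With n = 30 the gap is 9 to 11 drop-outs, and its probability is 0.119 at 20%, 0.276 at 25%, 0.409 at 30%, 0.430 at 35% and 0.337 at 40%. The gap matters under either denominator.

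**Where the 70% figure sits.** The complement of 70% retention is 30% drop-out, or 18 of 60. Because the proceed limit is strict, 18 is the first count in the gap. One fewer drop-out (17 of 60 = 28.3%) would be in the proceed band.

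**What is counted.** Section 15.1 speaks of drop-out from the RCT without naming a numerator or denominator. Only the intervention arm can finish the intervention (section 5.3) or miss coaching contacts (section 10.2), because section 11.3 says that controls do not receive the intervention. Read together, the three sections do not say how a control participant becomes a drop-out, or whether controls are in the denominator.

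**The case against.** The strongest reply is that the practical damage is limited. A result in the gap is far below the stop limit, so only modify versus proceed is open. The study is a feasibility study without formal hypothesis testing. A steering committee with an independent chair and an independent statistician discusses the results before publication (section 22.2). If retention is good, the gap is rarely reached: 4% at a true drop-out of 20%. Section 4 reports high retention in the earlier 3-month exercise trial. All of this stands and narrows the consequence, but none of it supplies the missing outcome.

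Three stronger readings are tempting, and the documents do not support them.

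- A reader might infer that the rule fails at the trial's expected result. Section 14.3 uses 70% only to illustrate precision for the cohort of 120. It is not called an expectation and does not concern the RCT. It also touches only the lower edge of the gap.
- A reader might infer that the whole decision, including stopping, could go unanswered. The stop limit is clear, and a result in the gap does not reach it.
- A reader might infer that the rule pools both arms, so that good control retention hides failure in the intervention arm. For example, 15 of 30 plus 2 of 30 is 17 of 60 = 28.3%, which would read as proceed. That is possible under one reading of section 15.1, but sections 5.3 and 10.2 point towards the intervention arm alone, and the rates in the example are invented. What the text supports is that drop-out and its denominator are not defined consistently.

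**Conclusion.** The defect is real and lies in the current text: the rule has no outcome for drop-out from 30% to under 40%. With 60 participants in the denominator and independent drop-outs, the chance of a result without an assigned outcome is 4% at a true drop-out of 20%, rises to 58% at 35%, and is 41% at 40%. Those true rates are assumptions, since the protocol gives no forecast for the RCT. The open choice is modify versus proceed unchanged. Alongside this, the quantity to which the rule applies is not defined in a way that covers controls. Neither point depends on 70% being an expected rate or on the arms being pooled.

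**What to change.** Before any 12-month data are reviewed, amend the sentence in section 15.1 as follows.

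- Reconcile the 30% and 40% limits so that every drop-out rate has one outcome. The document does not show which limit was intended, so the sponsor should confirm it. The cautious closure is under 30% proceed, 30% to 60% inclusive modify, over 60% no progression.
- State the numerator and denominator of drop-out from the RCT, including what counts as drop-out in a control participant, and align this with sections 5.3 and 10.2.
- Report drop-out by arm next to the overall figure.

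The chance of a result without an assigned outcome then becomes zero at every true rate. The cost is one amended sentence and the loss of some freedom: if the gap is closed at 30%, results of 30% to under 40% are fixed as modify and can no longer be read as proceed.

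Applying the bands to each arm and acting on the worse result is not part of this correction. That would be a new decision rule with a real price. Suppose that proceeding required under 30% both overall and in the intervention arm. Its chance would then fall from 0.78 to 0.61 with 25% true drop-out in both arms, and from 0.96 to 0.43 with 30% in the intervention arm and 10% in control (assumed rates, 30 per arm).

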# 5.3 Primary outcomes measure(s)

The primary outcome measures for this trial are focused on feasibility of the 12-month physical activity intervention.

- Recruitment rate will be assessed using site recruitment logs.
- Retention rate will be measured as the percentage of individuals who completed the intervention.
- Adherence rates will be defined as percentage of intervention sessions completed,
- Safety will be assessed through monthly documentation completed by therapists administering the intervention, which captures information on falls history, medication

changes, healthcare service use and hospital admissions (classified as serious adverse events).

- Fidelity of the interventions will be assessed via review of coach documentation and activity monitor data.
- Data completeness will be assessed by the percentage of data entered into the database.

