#### 9.5.2 Randomisation

The randomisation will be stratified by country. Participants within intervention countries will be randomised in a 1:1 ratio to receive the intervention or continue with their current regime of physical activity. A minimisation technique will be used for randomisation to ensure a similar distribution of selected participant factors between trial groups. The first participant is truly randomly allocated; for each subsequent participant, the treatment allocation that minimises the imbalance on the selected factors between groups at that time is selected. That allocation may then be used, or a choice may be made at random with a heavy weighting in favour of the intervention that would minimise imbalance (for example, with a probability of 0.8). The participant factors to be balanced in the nested RCT will be age (above or below age 50 years), gender and motor impairment (above or below UHDRS total motor score 40). The randomisation process will be automated via the PACE-HD database.

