#### 10.2 Loss to follow up

For the longitudinal observation study we do not anticipate a high rate of loss to follow up due the participant's ongoing involvement in Enroll-HD. We will adhere to the Enroll-HD protocol for managing lost to follow up participants in the observational cohort.

For participants in the nested RCT, participants will be deemed to be lost to follow up if they fail to attend more than 4 consecutive coaching contact sessions.

As this is a pragmatic trial, if a participant meets the criterion of lost to follow up, no further direct efforts will be made to engage with that participant. As all participants will be participants of Enroll-HD, we will be able to obtain a proportion of 12-month assessment data for all participants unless they are lost to follow up in the Enroll-HD study. Remote data from FitBit activity monitors will also be collected from those lost to follow up.

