# 11.3 Intervention comparator

#### Nested RCT

Those participants in the nested RCT randomised to activity as usual will not receive the physical activity intervention and will be asked to continue with their usual level of physical activity for the 12 month follow up period. They will not receive home visits from the intervention delivery staff (physical therapists), but they will be asked to record their activity monthly in paper diaries which will be sent to them. These participants will also receive monthly prompts via their preferred method of communication (e-mail/ telephone/ text messaging) to remind them to complete and return the diaries to their local coordinating centre in the stamped, addressed envelope provided. Their activity will not be monitored with the use of devices outside the week long activity monitoring period using Gene-activ devices that all participants will undertake.

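### The progression rule judges the intervention on drop-out from the RCT without naming the arm or defining drop-out; read over both arms, it can pass an intervention that half its recipients leave

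*Protocol*

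**What the plan says.** The progression criteria stand in the last paragraph of Protocol section 15.1, under the RCT analysis. There are three bands:

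- Stop: "over 60% drop out from the RCT at 12 months will mean no progression".
- Change: "between 40 and 60 % drop out will mean that changes to the intervention and/or follow-up procedures will be required".
- Proceed: "less than 30% drop at 12 months will indicate that the intervention is suitable for further evaluation without modification".

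The only stated input is drop-out from the RCT. The only stated output of the lowest band is a conclusion about the intervention. The RCT has 30 participants per arm (section 6), randomised 1:1 (section 9.5.2).

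Two other sections define related terms, and section 15.1 refers to neither:

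- Section 5.3: "Retention rate will be measured as the percentage of individuals who completed the intervention".
- Section 10.2, for the nested RCT: "participants will be deemed to be lost to follow up if they fail to attend more than 4 consecutive coaching contact sessions".

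Section 11.3 says that controls "will not receive the physical activity intervention and will be asked to continue with their usual level of physical activity".

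**The concern.** The rule draws a conclusion about one arm's treatment from a quantity that, read plainly, comes half from the other arm. Sections 5.3 and 10.2 can be applied only to people who are offered the intervention. Under 10.2 a control has no coaching session to miss and could be counted as lost only by some route that the section does not describe, such as withdrawal under section 10.1. It is therefore unclear who is in the denominator and what counts as an event.

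This matters because it is the protocol's only stated progression rule, and the background material names the feasibility of exercise beyond three months as an open question. If controls mostly stay, their retention dilutes losses among those asked to exercise for a year. An intervention whose own drop-out lies in the band requiring changes could then go forward unmodified. Two analysts could also apply the same sentence to the same data and report opposite verdicts.

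**Working it through.** **Inputs from the protocol.** 30 per arm, 60 in total (section 6). Bands: below 30%, 40–60%, above 60% (section 15.1). Section 14.3 gives ±8.2 points for 70% retention with 120 participants.

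**The plan's own figure.** The 95% half-width is 1.96 × √(p(1−p)/n). With p = 0.70 and n = 120: 1.96 × √(0.21/120) = 0.082. The stated 8.2% is reproduced. The same formula gives 0.116 at n = 60 and 0.164 at n = 30.

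**What the bands mean in counts.** Below 30% of 60 is at most 17 drop-outs (18/60 is exactly 30%). Below 30% of 30 is at most 8 (9/30 is exactly 30%).

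**Same data, two readings.**

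| Intervention | Control | Whole RCT | Verdict, whole RCT | Intervention arm | Verdict, intervention arm |
|---|---|---|---|---|---|
| 15/30 | 2/30 | 17/60 = 28.3% | without modification | 50% | changes required |
| 16/30 | 1/30 | 17/60 = 28.3% | without modification | 53% | changes required |
| 17/30 | 0/30 | 17/60 = 28.3% | without modification | 57% | changes required |
| 15/30 | 3/30 | 18/60 = 30.0% | none stated (30–40% has no band) | 50% | changes required |

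With equal arms, the whole-RCT rate is the average of the two arm rates. It is below 30% when the arm rates sum to less than 60%. Intervention drop-out of 50% passes only if control drop-out is below 10%; 45% passes only if it is below 15%.

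**How likely a pass is.** The protocol gives no expected drop-out by arm, so the rates below are assumptions shown over a range. Let X be Binomial(30, p for the intervention arm) and Y be Binomial(30, p for the control arm), independent. The whole-RCT probability is P(X + Y ≤ 17) = Σ P(X = i) × P(Y ≤ 17 − i), for i from 0 to 17. The intervention-arm probability is P(X ≤ 8).

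| True intervention drop-out | Control 0% | 5% | 10% | 20% | 30% | Intervention arm alone |
|---|---|---|---|---|---|---|
| 40% | 0.98 | 0.91 | 0.79 | 0.45 | 0.17 | 0.09 |
| 45% | 0.93 | 0.80 | 0.63 | 0.29 | 0.09 | 0.03 |
| 50% | 0.82 | 0.63 | 0.44 | 0.16 | 0.04 | 0.008 |

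The whole-RCT reading is far more permissive when controls stay. Most of the difference goes as control drop-out approaches 30%.

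**The case against.** **Pooling is not stated.** A reader might infer that the protocol prescribes combining the arms. It does not. It says drop-out from the RCT and leaves the denominator open, and the definition in section 5.3 allows an intervention-only reading. This stands, and it limits the point: the defect is an undefined rule whose plain reading misfires. It does not clear the rule, because the two readings give opposite verdicts on 15/30 and 2/30.

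**Control drop-out is relevant.** Section 5.1 sets the primary objective as feasibility of the nested randomised trial, and a later trial would also have to keep its controls. Controls are not free of burden either: they keep diaries, have telephone reviews and attend a 6-month assessment. This stands. Whole-RCT drop-out belongs in the rule, but it cannot alone carry a verdict on the intervention.

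**The reverse error.** A reader might also infer that heavy loss of controls would force changes to an intervention that was well tolerated. The text does not support this. The middle band requires changes to the intervention and/or follow-up procedures, so control losses can be answered through follow-up alone.

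**Other feasibility outcomes.** It is tempting to read the rule as excluding adherence, safety and fidelity from the decision. Section 15.1 gives them no threshold but does have them summarised, nothing says that they will be disregarded, and the SAP is not shown. Whether to add criteria on them is a matter of preference and is no error here.

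**Dependence on assumptions.** The misleading pass needs a large gap between arms, and the protocol gives no figure from which to judge that gap. This stands.

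**Conclusion.** The point holds as a should-fix. Section 15.1 words a conclusion about the intervention on a drop-out rate with no stated arm, definition or denominator. On the plain reading, the intervention can pass without modification while 50% to 57% of its recipients drop out, provided that at most two controls do (none at 57%). At an assumed 45% intervention drop-out, the chance of that verdict is 0.63, 0.29 or 0.09 as control drop-out goes from 10% to 20% to 30%, against 0.03 on the intervention arm alone.

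These probabilities rest on assumed arm rates, independent participants and full recruitment of 30 per arm. The conflict between readings rests on none of them, since it follows from the counts. This is a feasibility study without formal hypothesis testing, so no effect estimate is affected; what is at risk is the progression decision.

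**What to change.** Amend section 15.1 before outcome data are reviewed:

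1. Define drop-out so that it can be applied to both arms, for example as withdrawal from the trial or no month-12 PACE-HD assessment, and state how this relates to sections 5.3 and 10.2. Section 10.2 expects some Enroll-HD data even from people lost to follow-up, so say whether those data alone count as retention.
2. Read the bands twice: on the intervention arm (denominator 30) for the verdict on the intervention, and on the whole RCT (denominator 60) for the verdict on follow-up procedures and trial feasibility.
3. Let the less favourable result govern progression.
4. Assign the 30–40% range, with its end points, to a band. Otherwise step 3 is undefined whenever either reading falls there. With a true 30% drop-out, an arm of 30 has 9, 10 or 11 drop-outs, which is that range, with probability 0.41.

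The cost is a few sentences and no new data. The intervention-arm reading is less precise: a half-width of about 16.4 points at 70% retention, against 11.6 for the whole RCT. A pass also becomes somewhat harder to reach. If true drop-out is 20% in both arms, the chance of a pass falls from 0.96, P(X + Y ≤ 17), to 0.86, P(X ≤ 8 and X + Y ≤ 17).
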